### **5.3. Analysis Populations for Part B**

All participants who are enrolled in Part A and continues to Part B will be considered into analysis populations for Part B. SOT recipients who completed primary series vaccination with an mRNA or non-mRNA COVID-19 vaccine outside of the study who consent to receive BD in Part B will be included in Part B analysis populations.

#### **5.3.1. Modified Intent-to-Treat Set (Part B)**

The mITT Set (Part B) consists of all participants in the Safety Set who received BD and had no immunologic or virologic evidence of prior COVID-19 (ie, negative RT-PCR test and bAb against SARS-CoV-2 nucleocapsid (as measured by Roche Elecsys Anti-SARS-CoV-2 assay)) below LOD or LLOQ at pre-booster before the BD.

#### **5.3.2. Per-Protocol Set (Part B)**

The PP Set (Part B) includes all participants in the mITT set (Part B) who received planned BD per schedule and had no major protocol deviations that impact critical or key data.

#### **5.3.3. Per-Protocol Immunogenicity Set (Part B)**

PP Immunogenicity Set (Part B) includes all participants in the mITT Set (Part B) who received planned BD per schedule, and SOT recipients who completed primary series vaccination with an mRNA or non-mRNA COVID-19 vaccine outside of the study that are in the mITT Set (Part B). The participants who complied with the timings of immunogenicity blood sampling to have post-booster results available for at least one assay component corresponding to the immunogenicity analysis objective, and participant had no major protocol deviations that impact immune response during the period corresponding to the immunogenicity analysis objective will be included.

The PP Immunogenicity Set (Part B) will serve as the primary analysis population for the analysis of SARS CoV 2-specific bAb and nAb immunogenicity data in Part B.

Confidential

## 5.4. Solicited Safety Sets

The Solicited Safety Sets are considered relative to each (first, second, third, booster) injection, and consist of all participants who received the study injection (Safety Set) and contributed any solicited AR data following that injection. SOT recipients who completed primary series vaccination with an mRNA or non-mRNA COVID-19 vaccine outside of the study will be included in the Booster Injection Solicited Safety Set if received BD and contributed AR data following BD. The Solicited Safety Set will be used for the analyses of solicited ARs. The following Solicited Safety Sets are defined for each injection separately.

The **First Study Injection Solicited Safety Set** consists of all subjects in the Safety Set who have received the first study injection and have contributed any solicited AR data from the time of first study injection through the following 6 days.

The **Second Study Injection Solicited Safety Set** consists of all subjects in the Safety Set who have received a second study injection and have contributed any solicited AR data from the time of second study injection through the following 6 days.

The **Third Study Injection Solicited Safety Set** consists of all subjects in the Safety Set who have received a third study injection and have contributed any solicited AR data from the time of third study injection through the following 6 days.

The **Booster Injection Solicited Safety Set** consists of all subjects in the Safety Set who have received a BD and have contributed any solicited AR data from the time of BD through the following 6 days.

The **Any Study Injection Solicited Safety Set** is used to summarize certain endpoints after any injection and is the logical union of the First Injection Solicited Safety Set, and, when applicable, the Second Study Injection Solicited Safety Set, the Third Study Injection Solicited Safety Set, and the Booster Injection Solicited Safety Set.

## 6. Statistical Analysis

### 6.1. General Considerations

The schedule of assessments is provided in Appendix 1 of Protocol Amendment 4.

**Continuous variables** will be summarized using the following descriptive summary statistics: the number of subjects (n), mean, standard deviation (SD), median, minimum (min), and maximum (max).

Confidential

**Categorical variables** will be summarized using counts and percentages.

**Baseline value**, unless otherwise specified, is defined as the most recent non-missing measurement (scheduled or unscheduled) collected before the first dose of IP.

**Pre-booster baseline value** is defined as the most recent non-missing measurement (scheduled or unscheduled) collected before the BD on BD-Day 1.

For the summary statistics of all numerical variables unless otherwise specified, the display precision will follow programming standards. See [Appendix A](#) for variable display standards.

When count data are presented, the percentage will not be displayed when the count is zero in order to draw attention to the non-zero counts. A row denoted “Missing” will be included in count tabulations where specified on the shells to account for dropouts and missing values. The denominator for all percentages will be the number of subjects in the specified group within the analysis set of interest, unless otherwise specified.

**Baseline SARS-CoV-2 status** is determined by using virologic and serologic evidence of SARS-CoV-2 infection on or before Day 1.

Positive SARS-CoV-2 status at Baseline is defined as a positive RT-PCR test for SARS-CoV-2, and/or a positive serology test based on bAb specific to SARS-CoV-2 nucleocapsid (as measured by Roche Elecsys Anti-SARS-CoV-2 assay) on or before Day 1.

Negative status at Baseline is defined as a negative RT-PCR test for SARS-CoV-2 and a negative serology test based on bAb specific to SARS-CoV-2 nucleocapsid (as measured by Roche Elecsys Anti-SARS-CoV-2 assay) on or before Day 1.

**Pre-booster SARS-CoV-2 status**, is determined by using virologic and serologic evidence of SARS-CoV-2 infection prior to the BD in Part B.

Positive pre-booster SARS-CoV-2 status is defined as a positive RT-PCR test for SARS-CoV-2, and/or a positive serology test based on bAb specific to SARS-CoV-2 nucleocapsid (as measured by Roche Elecsys Anti-SARS-CoV-2 assay) on or before the date of BD (BD-Day 1).

Negative pre-booster SARS-CoV-2 status is defined as no virologic or serologic evidence of SARS-CoV-2 infection on or before BD-Day 1 (pre-booster), i.e. RT-PCR result is not positive if available at BD-Day 1 and a negative bAb specific to SARS-CoV-2

Confidential

nucleocapsid (as measured by Roche Elecsys Anti-SARS-CoV-2 assay) on or before BD-Day 1.

**Study day relative to the first study injection** will be calculated as below:

- a) Study day prior to the first study injection will be calculated as: date of assessment/event – date of the first study injection;
- b) Study day on or after the date of the first study injection will be calculated as: date of assessment/event – date of the first study injection + 1.

**Study day relative to the most recent study injection** will be calculated as below:

- a) Study day prior to the first study injection will be calculated as: date of assessment/event – date of the first study injection;
- b) Study day on or after the date of the first study injection but before the second study injection (if applicable) will be calculated as: date of assessment/event – date of the first study injection + 1;
- c) Study day on or after the date of the second study injection but before the third study injection (if applicable) will be calculated as: date of assessment/event – date of the second study injection + 1;
- d) Study day on or after the date of the second study injection will be calculated as: date of assessment/event – date of the second study injection + 1 provided that if study day is on the same day as the second study injection, the time is after the second study injection time;
- e) Study day on or after the date of the third study injection but before the BD (if applicable) will be calculated as: date of assessment/event – date of the third study injection + 1;
- f) Study day on or after the date of the third study injection will be calculated as: date of assessment/event – date of the third study injection + 1 provided that if study day is on the same day as the third study injection, the time is after the third study injection time;
- g) Study day on or after the date of the BD will be calculated as: date of assessment/event – date of the BD + 1 provided that if study day is on the same day as the BD, the time is after the BD time.

Confidential

**For calculation regarding antibody levels/concentrations**, antibody values reported as below LLOQ will be replaced by  $0.5 \times \text{LLOQ}$ . Values that are greater than the upper limit of quantification (ULOQ) will be used as available. Values that are reported as greater than ULOQ ( $>\text{ULOQ}$ ) without actual values will be replaced by ULOQ for analysis. Missing results will not be imputed, unless otherwise specified.

**The following Analysis Stages** will be defined for use in this study:

- Up to 28 days after any vaccination:

This stage starts at the day of each vaccination and continues through the earliest date of (the day of each vaccination and 27 subsequent days, next vaccination [if applicable]). This analysis period will be used as the primary analysis period for safety analyses (including unsolicited AEs), except for solicited ARs, unless specified otherwise.

- Throughout the study period:

For subjects in Part A, this analysis period starts at the first study injection on Day 1 and continues through the earliest date of study completion (or prior to BD), discontinuation from the study, or death.

For subjects in Part B, this analysis period starts at the BD on BD-Day 1 and continues through the earliest date of study completion, discontinuation from the study, or death.

For subjects in Part A and Part B, this analysis period starts at the first study injection on Day 1 and continues through the earliest date of study completion, discontinuation from the study, or death.

**Unscheduled visits:** Unscheduled visit measurements will be included in the analysis as follows:

- In scheduled visit windows per specified visit windowing rules.
- In the derivation of baseline/last on-treatment measurements.
- In the derivation of maximum/minimum on-treatment values and maximum/minimum change from baseline values for safety analyses.
- In individual subject data listings as appropriate.

**Visit windowing rules:** The analysis visit windows for protocol-defined visits are provided in [Appendix B](#). Results in previously vaccinated participants who received a third

Confidential

injection in the study will be presented in tables, figures, and listings at study visits related to the third injection.

**Incomplete/missing data** will be handled by the following conventions:

- Imputation rules for missing prior/concomitant medications, non-study vaccinations and procedures are provided in [Appendix C](#).
- Imputation rules for missing AE dates are provided in [Appendix C](#).
- For laboratory assessments, if the majority of results are indefinite, imputation of these values will be considered. If the laboratory results are reported as below the LLOQ (e.g., <0.1), the numeric values will be imputed by  $0.5 \times \text{LLOQ}$  in the summary. If the laboratory results are reported as greater than the ULOQ (e.g., >3000), the numeric values will be imputed by ULOQ in the summary.
- For immunogenicity assessments, imputation of missing results will be considered based on description in [Section 6.4](#).
- Other incomplete/missing data will not be imputed, unless specified otherwise.

**Participant groups** will be summarized according to the schema below.

- Transplant status:
  - SOT Kidney
  - SOT Liver
  - SOT Total
  - 2-Dose Healthy
- Dosing regimens:
  - Overall
  - Unvaccinated SOTs Who Received 2 Doses
  - Unvaccinated SOTs Who Received 3 Doses
  - Previously Vaccinated SOTs Who Received a Third Dose
  - Total SOTs Who Received 3 Doses
  - Primary Series All SOTs Who Received a Booster Dose
- Primary Series All SOTs Who Received a Booster Dose:
  - Overall
  - 3-Dose Moderna
  - 3-Dose Pfizer

Confidential

- Other

Unless otherwise mentioned, the results of the analyses will be summarized according to the participant groups above. Subjects under the same dosing regimen may be combined for analyses regardless of BD. Participants that received booster may be analyzed separately from participants that did not receive booster.

**Subgroup analyses** for safety and immunogenicity endpoints may be analyzed in select subgroups specified below as applicable:

- Age (18 to < 65,  $\geq$  65)
- Time of post-transplantation (< 2,  $\geq$  2 years)
- Baseline SARS-CoV-2 Status in each part (Positive, Negative) (for safety data)
- Sex (Male, Female)
- Race (White, Communities of color)
- Anti-metabolite immunosuppression (Yes, No)
- Combination of immunosuppressants (Mycophenolate, Tacrolimus, and Prednisone; Mycophenolate and Tacrolimus; Tacrolimus; and Other)
- Previous induction therapy (Basiliximab or other monoclonal antibody; Basiliximab or other monoclonal antibody with steroids; Thymoglobulin; Thymoglobulin with steroids; or steroids alone)

All analyses will be conducted using SAS Version 9.4 or higher.

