3.2. Scientific Rationale for Study Design

The study vaccine, mRNA-1273, is currently being evaluated in a pivotal Phase 3 efficacy, safety, and immunogenicity study in an adult population at high risk of COVID-19 disease (Study P301). Success criteria for early efficacy were met at first interim analysis based on 95 adjudicated cases with a vaccine efficacy of 94.5% (95% CI: 86.5%, 97.8%; one-sided p value < 0.0001). Immunocompromised individuals were excluded from this study.

The current study aims to describe the safety and Ab responses elicited following the last dose of vaccine among adult kidney and liver transplant recipients evaluated against the Ab responses of healthy adult participants in this study and in Study P301 (if available at the time of database lock). This study is expected to provide initial clinical information whether vaccination with mRNA-1273 can induce vaccine response in this population of immunocompromised participants, and whether 3 doses of vaccine induces a greater response than a 2-dose regimen. Recent data based

on post-EUA experience show that solid organ transplant recipients' response to mRNA-based COVID-19 vaccines were substantially lower compared to what has been reported in the general population with antibody responses detectable in only 30-60% after 2 doses ([Benotmane et al 2021](#); [Boyarsky et al 2021b](#), [Grupper et al 2021](#); [Marinaki et al 2021](#)).

A small case series which evaluated the antibody responses and vaccine reactions in 30 solid organ transplant recipients who had suboptimal response to standard vaccination show that SOT recipients who had low-positive antibody response before the third dose had high-positive antibody titers after dose 3 and some of those who had negative antibody response had either low-to high-positive antibody response after dose 3 ([Werbel et al 2021](#)).

In addition, a recently published article described a double-blind, randomized, controlled trial of a third dose of mRNA-1273 vaccine (Moderna) as compared with placebo (NCT04885907; [Hall et al 2021](#)). The results demonstrated that a third dose of mRNA-1273 vaccine in transplant recipients elicited a substantially higher immune response than placebo, as determined in the analysis of both primary and secondary trial endpoints. The third dose was considered safe when risk versus benefit was considered.

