Recording of suspected AND confirmed organ transplant rejection ¹⁷	X	X	X	X	X	X	X
Recording of concomitant medications and nonstudy vaccinations ¹⁷	X	X	X	X	X	X	X
Recording of concomitant immunosuppressant medications ¹⁸	X	X	X	X	X	X	X

Abbreviations: AE = adverse event; AESI = adverse event of special interest; AR = adverse reaction; BD = booster dose; C = clinic visit; D = day; eDiary = electronic diary; ICF = informed consent form; MAAE = medically attended AE; NP = nasopharyngeal; SAE = serious adverse event; SC = safety (phone) call; SOTr = solid organ transplant recipients.

Note: In accordance with FDA Guidance on Conduct of Clinical Trials of Medical Products during COVID-19 Public Health Emergency (DHHS 2020), investigators may convert study site visits to home visits or telemedicine visits with the approval of the Sponsor.

1. A BD may be administered to all eligible participants who are currently enrolled in Part A or Part B provided there are no current contraindications for further dosing ([Section Error! Reference source not found.](#)). A participant who is currently in the Convalescent Period may come in for a BD-1 visit and receive a BD as long they are no longer symptomatic, and this includes the possibility for a Convalescent Visit Day 28 to overlap and be combined with a BD-1 visit. For eligible participants in Part A who are at least 4 months from completion of primary vaccination series who consent to receive BD, the study visit or follow-up 4 months after their last dose in Part A may overlap with BD-D1. In this case, a participant will need to come in for the BD-D1 visit at least 4 months after the last dose and then follow Part B.

2. Symptom-directed physical examination will be performed at the BD-Day 1. At visits BD-2 (BD-D29), and BD-3 (BD-D181), a symptom-directed physical examination may be performed at the discretion of the investigator. Any clinically significant finding identified during a study visit should be reported as a MAAE.
3. On dosing day before injection, the arm receiving the injection should be examined and the associated lymph nodes should be evaluated.

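### SAP 6.1 contradicts itself on pre-booster SARS-CoV-2 status: a participant PCR-positive in Part A but nucleocapsid-negative at the booster is both positive and negative

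*SAP*

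**What the plan says.** SAP 6.1 (General Considerations) gives two definitions.

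- **Positive.** "Positive pre-booster SARS-CoV-2 status is defined as a positive RT-PCR test for SARS-CoV-2, and/or a positive serology test" for nucleocapsid antibody, with the time limit "on or before the date of BD (BD-Day 1"). An illness-visit swab in Part A falls inside that limit.
- **Negative.** The sentence opens broadly: "Negative pre-booster SARS-CoV-2 status is defined as no virologic or serologic evidence of SARS-CoV-2 infection on or before BD-Day 1 (pre-booster"). An i.e. clause then spells this out: "RT-PCR result is not positive if available at BD-Day 1 and a negative bAb specific to SARS-CoV-2" nucleocapsid, on or before BD-Day 1. Here the RT-PCR is tied to BD-Day 1 and may be absent.

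SAP 5.3.1 defines the mITT Set (Part B) without referring to the 6.1 status. Members "received BD and had no immunologic or virologic evidence of prior COVID-19 (ie, negative RT-PCR test and bAb against SARS-CoV-2 nucleocapsid" below the assay limit at pre-booster. It does not say which RT-PCR results count.

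SAP 5.3.3 draws the PP Immunogenicity Set (Part B) from that mITT set and makes it the primary population for Part B antibody data. SAP 6.5 excludes participants with positive or missing pre-booster status from the Part B infection analysis and refers to 6.1 for the definition.

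**The concern.** A status variable should put each participant in one category. Here the broad and narrow wordings diverge for people infected during Part A who have no nucleocapsid antibody at the booster.

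The situation can arise. Protocol Table 10, footnote 1, states: "A participant who is currently in the Convalescent Period may come in for a BD-1 visit and receive a BD", subject to being symptom-free, and lets the day-28 convalescent visit be combined with BD-1. Part A participants enter Part B on active participation and dose interval (Protocol 4.2.1). The exclusion for known infection history (Protocol 4.1.1.2, criterion 1) is reapplied at booster entry only to Group B4 (Protocol 4.2.2).

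The primary Part B immunogenicity result is at stake: the nAb GMC 28 days after the booster in transplant recipients. Later steps offer no clear safeguard. The sensitivity analysis in SAP 6.4 uses the mITT Set (Part B), which would carry the same misclassification. The sample-eligibility rule in 6.4 concerns medications and vaccines, not infection. Nothing in the documents makes an infection a protocol deviation.

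**Working it through.** The plan gives no figure to reproduce, so the check is one of logic.

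**Step 1. Enumerate.** The inputs are an earlier Part A RT-PCR (positive or not), the BD-Day 1 RT-PCR (negative, positive or missing) and nucleocapsid antibody (negative or positive): 2 × 3 × 2 = 12 combinations. Three rules from 6.1 are applied to each: the positive definition, the opening clause of the negative definition, and its i.e. clause.

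- 8 combinations are positive on every rule: those with positive nucleocapsid antibody or a positive BD-Day 1 swab.
- 2 are negative on every 6.1 rule (rows A and B below).
- 2 conflict (rows C and D below).

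All four rows below are nucleocapsid-negative.

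| Row | Earlier RT-PCR | BD-Day 1 RT-PCR | 6.1 positive | 6.1 negative, opening clause | 6.1 negative, i.e. clause | 5.3.1 parenthesis |
|---|---|---|---|---|---|---|
| A | not positive | negative | no | yes | yes | met |
| B | not positive | missing | no | yes | yes | not met as worded |
| C | positive | negative | **yes** | no | **yes** | met if only the pre-booster swab is read |
| D | positive | missing | **yes** | no | **yes** | not met as worded |

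Rows C and D are the contradiction within 6.1. Rows B and D show the second mismatch: 6.1 tolerates a missing BD-Day 1 swab and 5.3.1 asks for a negative test. An earlier negative swab might stand in for it, but 5.3.1 does not say so.

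**Step 2. Trace to the primary set.** Row C could enter the mITT Set (Part B) under the parenthesis in 5.3.1. Row D could enter only if that set were programmed from the 6.1 i.e. clause. The opening clause of 5.3.1, which bars evidence of prior COVID-19, would exclude both. Whoever enters mITT (Part B) can reach the PP Immunogenicity Set (Part B) through 5.3.3.

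**Step 3. Sensitivity of the GMC.** Let f be the share of the analysed set that was previously infected and r the ratio of their geometric mean to that of the rest. Then log GMC = (1 − f) log G + f log(rG), so the GMC is multiplied by r^f. Both inputs are assumed; the documents supply neither.

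| f | r = 2 | r = 4 | r = 10 |
|---|---|---|---|
| 2% | 1.01 | 1.03 | 1.05 |
| 5% | 1.04 | 1.07 | 1.12 |
| 10% | 1.07 | 1.15 | 1.26 |
| 20% | 1.15 | 1.32 | 1.58 |

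The grid shows how the result would respond. It is not an estimate for this trial.

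**Step 4. Test the repair.** If any positive RT-PCR or nucleocapsid result on or before BD-Day 1 makes a participant positive, and negative means none of these, none of the 12 combinations is both. Rows C and D become positive and leave the set.

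**The case against.** The strongest reply is that the SAP, read as a whole, already excludes this participant. The positive definition covers any RT-PCR up to the booster date, and the opening clauses of the negative definition and of 5.3.1 both bar prior virologic evidence. On that view the i.e. clause is loose drafting.

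Much of this stands. A reader might infer that negative status rests only on the BD-Day 1 swab and nucleocapsid test, so that such participants do enter the primary set. The documents do not support that: three broader statements point the other way, and the nucleocapsid test covers results on or before BD-Day 1, not that day alone.

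It does not dispose of the point. An i.e. clause purports to say what the preceding words mean, and it is the part most easily turned into code. The Part A negative definition in 6.1 neither ties RT-PCR to a single visit day nor tolerates a missing result, so the pre-booster wording looks deliberate.

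Four further inferences should be resisted.

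- **A numerical bias.** The Protocol's statement "with antibody responses detectable in only 30-60% after 2 doses" concerns response to mRNA vaccination. It is not evidence on nucleocapsid seroconversion after infection. It would also be awkward to assume that people who made no nucleocapsid antibody have much higher neutralising titres.
- **An effect on Group B5.** The primary Part B nAb endpoints are in transplant recipients only, so healthy adults are outside them.
- **A distorted comparison between the two booster endpoints.** No between-group comparisons are planned (SAP 4.2). Group B4 may also include three-dose Moderna recipients, so it does not map onto one endpoint.
- **A conflict between 6.1 and 6.5 on a missing swab.** SAP 6.5 excludes missing status, not a missing RT-PCR. Under the 6.1 i.e. clause a missing swab with negative serology gives a negative status.

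**Conclusion.** Wrong as written: an internal contradiction. SAP 6.1 classes one type of participant as both positive and negative, and 5.3.1 neither resolves this nor agrees with 6.1 on a missing BD-Day 1 swab. Whether previously infected participants reach the primary Part B immunogenicity set depends on which clause is programmed.

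If the i.e. clause is used, the booster nAb GMC in Groups B2 and B3 would be raised, provided prior infection goes with higher titres in these participants. The size cannot be estimated, because the documents give no rate of PCR-confirmed infection in Part A, no rate of nucleocapsid non-response after infection and no titre ratio. The effect could be small. The point deserves correction because it concerns who is in a primary analysis set and is easily settled in advance.

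**What to change.** Before database lock, put one definition in SAP 6.1:

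- **Positive:** any positive RT-PCR (scheduled, illness or convalescent visit, central or local laboratory) or any positive nucleocapsid result, on or before BD-Day 1.
- **Negative:** none of these, with a nucleocapsid result available at BD-Day 1.
- **Missing BD-Day 1 RT-PCR:** one stated rule, applied everywhere.

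Replace the parenthesis in 5.3.1 with a reference to that status, and have 6.5 cite the same status, including what counts as missing.

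No new data are needed: illness-visit and convalescent swabs are already collected (Protocol 7.1.6 and 7.3.2). The cost is SAP wording, and a few participants may leave the Part B per-protocol sets.
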